**List of Abbreviations**

ACTSI	Atlanta Clinical & Translational Science Institute
AE	Adverse Event
CDC/VIS	Centers for Disease Control and Prevention/Vaccine Information Statement
CFR	Code of Federal Regulations
CIERS	Center for Influenza Excellence in Research and Surveillance
CoC	Certificate of Confidentiality
CPM	Clinical Project Manager
CRF	Case Report Form
DMID	Division of Microbiology and Infectious Diseases, NIAID, NIH
eCRF	Electronic CRF
FDA	Food and Drug Administration
FISMA	Federal Information Security Management Act
GCP	Good Clinical Practice
GCRC	General Clinical Research Center of Emory University
HA	Hemagglutinin
HHS	Health and Human Services
HI	Hemagglutination Inhibition
HIPAA	Health Insurance Portability and Accountability Act
ICH	International Conference on Harmonisation
IDS	Investigational Drug Services
IMGT	Immunogenetics Information System
IM	Intramuscular
IRB	Institutional Review Board
MI	Milliliter
MO	Medical Officer
MOP	Manual of Procedures
NA	Neuraminidase
NGS	Next Generation Sequencing
NIAID	National Institute of Allergy and Infectious Diseases, NIH
NIH	National Institutes of Health
NSAID	Non-steroidal anti-inflammatory drug
PHI	Protected Health Information
QIV	Quadrivalent inactivated vaccine
RedCap	Research Electronic Data Capture
SAE	Serious Adverse Event
SMC	Safety Monitoring Committee
TIV	Trivalent Inactivated Vaccine
US	United States
VAERS	Vaccine Adverse Event Reporting System
WNL	Within Normal Limits

**Title:** Evaluation of Human Immune Responses to Influenza Virus Vaccination in Healthy Volunteers

**Population:** Male and female individuals aged 18-49; target enrollment is up to a total of 70 subjects.

**Number of Sites:** 1

**Study Duration:** 6 years

**Participant Duration:** 180 days (6 months)

**Objectives:**

Primary Objectives:

To characterize HA-specific plasmablasts and memory B cells after influenza vaccination

Secondary Objective:

To investigate the longevity of humoral immunity to influenza virus in humans

**Study Summary:**

[figure not shown]
This is an open label single arm observational study of longitudinal immunologic responses to influenza vaccine in healthy adult subjects. This study will enroll males and non-pregnant females, 18-49 years old. The subjects will be screened at enrollment with a history and physical exam and laboratory testing to ensure they are healthy enough to participate. Qualifying subjects will be vaccinated with an FDA approved seasonal inactivated influenza vaccine (IIV) according to the package insert. Approximately 450 ml of blood will be collected for the research assays during the course of the study. Specifically, 16 ml will be collected for screening; 48ml will be collected at enrollment; 96ml will be collected at visit days 7 and 14; and 64 ml will be collected at 28, 90, and 180 days post vaccination.

Due to the COVID-19 pandemic, all non-essential research was halted in mid-March 2020. New enrollments were placed on hold for this study. Follow-up visits were also halted, which impacted the timing of participants' subsequent follow-up visits. For this study, there are participants whose Day 180 visits were impacted. We will request an expansion of the study window for the participants whose visits were impacted. Additional details regarding this are detailed further in the protocol. None of the other visits were impacted.

The study will enroll 10 healthy volunteers per vaccination season in years 1, 2, and 4. For years 5 and 6, we anticipate enrolling a maximum of 20 participants for a total enrollment of up to 70

subjects. Individuals who complete the study will be given the option to re-enroll in subsequent years as long as they continue to meet all inclusion/exclusion criteria. Re-enrolling subjects will be re-consented, given new subject identifiers, and counted towards the enrollment number goal for each year of participation.

### Schematic of Study Design:

### Blood Draws

Clinical Group	Numbers	Timepoint (day)						
		Screen	0	7	14	28	90	180
Healthy Controls receiving inactivated influenza vaccine	10/year Years 1, 2, and 4 Maximum of 20/year for Years 5 and 6	16 ml	48ml	96ml	96ml	64ml	64ml	64ml

## 2 BACKGROUND INFORMATION AND SCIENTIFIC RATIONALE

### 2.1 Background Information

Annual influenza virus epidemics by subtype A viruses (H1N1 and H3N2), and/or influenza B viruses have been shown to cause substantial morbidity and mortality, exacting an average of 36,000 deaths and more than 200,000 hospitalizations in the US alone (1).

To combat this important public health threat, two types of inactivated influenza vaccines have been approved by the FDA: 1) a trivalent, inactivated vaccine (TIV); and 2) a quadrivalent inactivated vaccine (QIV). The TIV vaccine contains the hemagglutinin (HA) and neuraminidase (NA) proteins corresponding to the three influenza viruses predicted to be in circulation during the influenza season (two A strains and one B), and the quadrivalent type contains the HA and NA for an additional B strain. These vaccines induce predominantly HA-specific and NA-specific antibodies that are capable of virus neutralization. Antibodies to HA are critical to provide immune protection to the host against influenza virus infection, as this protein plays a key role in virus entry to initiate the replication cycle in the cell. A live attenuated vaccine has also been approved but this study will use only inactivated influenza vaccine.

Currently, the Advisory Committee on Immunization Practices of the CDC recommends that everyone aged 6 months or older in the United States receive the influenza vaccine on an annual basis (2). The recommendation for annual vaccination, regardless of previous vaccination history, is in part due to the constantly changing nature of the influenza strains in circulation. Through the processes of antigenic drift and antigenic shift, the viral HA protein is constantly changing to evade the antibody response. This requires that the formulation of the influenza vaccine must be updated each season. However, when the vaccine formulation remains unchanged from year to year, re-vaccination is still recommended because antibody levels decline over the course of a year (3).

In recent years it has become apparent that a significant fraction of the human antibody response to influenza targets highly conserved neutralizing epitopes on the virus (4). This raises the possibility that an optimally designed vaccine could elicit a broad immunity to the virus. If long lived antibody responses could be generated against these neutralizing epitopes through immunization, it could eliminate the need for yearly re-vaccination. The development of such a vaccine will therefore require an understanding of the factors that lead to the generation of long-lived antibody responses.

## 2.2 Scientific Rationale

The challenge of developing a broadly protective influenza vaccine stems from three main factors: first, the ever-evolving nature of influenza viruses which allows the virus to overcome pre-existing immunity; second, the fact that the majority of vaccine-elicited neutralizing antibodies are directed against epitopes within the hypervariable region of the HA globular head which facilitates the emergence of antibody-escape viral variants; and third, the apparent short half-life of vaccine-mediated protection, in some instances, even against matched virus strains, raising issues about the longevity of vaccine induced immune responses. Therefore, an ideal influenza vaccine should feature two improvements over the existing ones; it should be able to elicit neutralizing antibody responses against conserved HA epitopes to provide broad protection against diverse influenza virus strains and it should be able to induce long-lived antibody responses.

Generation of immunological memory is the hallmark of adaptive immune responses. Influenza vaccines work by activating antigen-specific B cells to proliferate and differentiate into plasmablasts (PBs) that secrete protective antibodies and memory B cells (MBCs) that can rapidly proliferate and differentiate into PBs upon re-encountering the immunizing antigen. A subset of the plasmablasts migrate to the bone marrow and become long-lived plasma cells (LLPCs) secreting antigen-specific antibodies for protracted periods of time. Memory B cells and long-lived PCs provide a remarkably stable immunological memory that can persist over 50 years after vaccination in humans. It remains unclear what factors direct the differentiation of activated, antigen-specific B cells into either memory B cells or plasmablasts and long-lived plasma cells. Studies in mice have suggested that the B cell repertoire in the memory B and the long-lived plasma cell compartments differ in terms of antigen-binding affinity and breadth. In this study, we will address the fundamental question of what determines the fate (plasmablasts vs. memory B cells) of antigen-specific B cells following vaccination in humans.

## 2.3 Potential Risks and Benefits

### 2.3.1 Potential Risks

The physical risk of drawing blood is local pain and bruising at the site of venipuncture. Qualified phlebotomists or designee will draw blood samples. Care will be taken to obtain these specimens in a safe and hygienic manner. A small number of people experience lightheadedness or fainting. There is a slight risk of infection. Repeated blood drawing may be associated with iron deficiency anemia. To avoid this risk, no more than 432 ml of blood will be obtained over a period of 180 days.

The side effects from inactivated influenza vaccine are generally mild. They include soreness at injection site (10-64% of subjects) that lasts <2 days. When the vaccine is given, the subject may feel a slight pain and burning during the injection. Fever, malaise and myalgia can occur after vaccination with inactivated influenza vaccine. These reactions begin 6-12 hours after vaccination

and can persist for 1-2 days. Allergic reactions rarely occur after influenza vaccination and are generally caused by residual egg proteins. Persons with a history of egg allergy will be excluded from study participation. Associated with the 1976 swine influenza vaccine, there is a slight risk of Guillain-Barre syndrome with the administration of the seasonal inactivated influenza vaccine. Persons with a history of Guillain-Barre syndrome will be excluded from study participation.

Occasionally, recipients of unadjuvanted licensed, inactivated influenza virus vaccines may develop influenza-like reactions, such as fever, feverishness (chills/shivering/sweating), fatigue (tiredness), malaise (general unwell feeling), myalgia (body aches/muscular pain), arthralgia (joint pain), headache, and/or nausea. Some subjects may develop reactions at the injection site, including pruritus (itching), ecchymosis (bruising), erythema (redness), induration (hardness)/swelling, pain, and/or tenderness. With unadjuvanted licensed, inactivated influenza virus vaccines most of these reactions peak in intensity in the first 24 hours after vaccination and usually disappear without treatment within 1 or 2 days. Analgesics (e.g., acetaminophen, or ibuprofen or similar non-steroidal anti-inflammatory drugs (NSAIDs)) and rest may generally relieve or lessen these reactions. Bruising can sometimes occur due to the vaccination procedure.

Acute and potentially life-threatening allergic reactions are also possible. Very rarely, occurring in about 1 in 4 million people given a vaccination, there can be a serious allergic reaction to a vaccine. These reactions can manifest as skin rash (hives), swelling around the mouth, throat or eyes (angioedema), difficulty breathing (bronchospasm), a fast pulse (tachycardia), or loss of blood pressure (hypotension). If these reactions occur, they can usually be stopped by the administration of emergency medications by the study personnel. As with any vaccine or medication, there is a very small chance of a fatal reaction (death), although researchers do not expect this to occur.

In addition, post-marketing surveillance indicates the following adverse events of special interest (AESI) as potential risks for the seasonal influenza vaccines: neuritis, convulsions, severe allergic reactions, syncope, encephalitis, thrombocytopenia, vasculitis, and Guillain-Barré syndrome. Reports of these reactions were rare; however, exact incidence rates cannot be precisely calculated.

During the swine influenza (H1N1) vaccine campaign of 1976, some recipients developed a paralytic illness called Guillain-Barré syndrome (GBS). GBS is an acute inflammatory neuropathy characterized by weakness, hyporeflexia or areflexia, and elevated protein concentrations in cerebrospinal fluid. The rate of GBS was significantly increased in individuals receiving the 1976 swine influenza (H1N1) vaccine at about 1 per 100,000 vaccine recipients. This syndrome has not been seen consistently with other influenza vaccines. Most persons who develop GBS recover completely, although the recovery period may be as little as a few weeks or as long as a few years. About 30% of those with GBS still have residual weakness after 3 years and about 3% may suffer a relapse of muscle weakness and tingling sensations many years after the initial attack. Intensive surveillance of GBS after administration of inactivated influenza vaccines since 1976 has shown a

slight increase in risk over background cases (more than one additional case of GBS per million persons) following vaccination, typically with onset within 6 weeks after vaccination (44). Interestingly, although vaccination rates have increased in the last 10 years the numbers of reported cases of vaccine-associated GBS have declined (45). A recent study in Canada showed that the 2009 H1N1 vaccine was associated with a small but significant risk of GBS in persons 50 years and older (46). An active, population-based surveillance study conducted during the 2009-2010 influenza season found less than 1 excess GBS case per million doses of 2009 H1N1 vaccine administered – a rate similar to that associated with some previously administered annual influenza vaccines (47-49). Another study using the Medicare system showed an elevated risk of GBS with 2009 monovalent H1N1 vaccination (incidence rate ratio = 2.41, 95% confidence interval: 1.14, 5.11; attributable risk = 2.84 per million doses administered, 95% confidence interval: 0.21, 5.48) (50). An international collaboration study also supported a conclusion of an association between 2009 H1N1 vaccination and GBS (51). It is unknown if the administration of the inactivated A/H7N9 vaccine to be used in this study will result in the incidence of GBS that was seen with the 1976 vaccine product as the mechanism leading to this response has not been completely elucidated.

Subjects will be asked to provide personal health information (PHI). All attempts will be made to keep this PHI confidential within the limits of the law. However, there is a chance that unauthorized persons will see the subjects' PHI. All records will be kept in a locked file cabinet or maintained in a locked room at the participating VTEU sites. Electronic files will be password protected. Only people who are involved in the conduct, oversight, monitoring, or auditing of this study will be allowed access to the PHI that is collected. Any publications from this study will not use information that will identify subjects by name. Organizations that may inspect and/or copy research records maintained at the participating sites for quality assurance and data analysis include groups, such as National Institute of Allergy and Infectious Diseases (NIAID) and Food and Drug Administration (FDA).

There may be other unknown risks, discomforts, or side effects.

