## 5 STUDY POPULATION

The study will enroll 10 healthy volunteers per vaccination season in years 1, 2, and 4, to analyze the immune response to influenza vaccination in healthy individuals. For years 5 and 6, we anticipate enrolling a maximum of 20 participants, to analyze the immune response to influenza vaccination in healthy individuals.

Total enrollment goal is up to a total of 70 subjects. Individuals who complete the study will be given the option to re-enroll in subsequent years as long as they continue to meet all inclusion/exclusion criteria. Re-enrolling subjects will be re-consented, given new subject identifiers, and counted towards the enrollment number goal for each year of participation.

- Males and non-pregnant females confirmed to be non-pregnant immediately prior to vaccination, aged 18 - 49, inclusive.
- Study subjects will be drawn from existing populations of students, staff, faculty, or volunteers at Emory University or other eligible healthy adults who may hear of the study by word of mouth.
- Study subjects will be recruited via word of mouth and placement of recruitment flyers in key locations on campus. Social media messaging via Facebook and Twitter will also be used in an effort to increase the number of enrollees into this study.

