## 7 STUDY SCHEDULE

### 7.1 Screening (Day -1 to day -30)

Potential participants will be screened for eligibility within 30 days prior to the administration of the study product. Screening period begins at screening visit and continues through enrollment visit. Qualified subjects will be scheduled for enrollment visit 1-day post screening visit through 30 days post screening visit. At screening, the following activities will be performed:

- Participants will be provided with a description of the study (purpose and study procedures) and asked to read and sign the informed consent form. The informed consent form will be signed prior to performing any study procedures, including any screening procedures.
- Complete medical history will be obtained by interview of participants to assure eligibility, including history of prior influenza vaccinations.
- All concomitant medications will be recorded on the appropriate data collection form.
- Demographic information will be collected from the participant.
- Eligibility criteria will be reviewed.
- A urine pregnancy test will be performed on all female participants of childbearing potential and must be negative.
- Approximately 16 ml (about 1 tablespoon) of venous blood will be collected for chemistry and hematology performed by the site laboratory. The results will be provided by the site laboratory and be reviewed by the principal investigator.
- Targeted physical exam, including height, weight and vital signs (oral or axillary temperature, pulse, blood pressure.).

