### 7.3 Follow-up and Final Visits

#### Follow-up visits: Days 7, 14, 28, 90, 180.

- Study participants will be asked to return for five follow up visits, with the respective window periods, per the table below:

Day	7	14	28	90	180
Time point					
Window	+/- 1	+/- 2	+/- 3	+/- 10	+/- 14 (a 90 day window expansion is being requested)
Blood Volume	96mL	96mL	64mL	64mL	64mL

- Medical history will be reviewed and updated as appropriate.
- All concomitant medications taken since the previous study visit will be recorded on the appropriate data collection form. Previously recorded medications will be updated as appropriate.
- Study personnel will discuss with participants and assess and record all AE/SAEs. Previously recorded AE/SAEs will be updated as appropriate.
- Approximately the amount of venous blood, as indicated by the table above, will be collected for research assays.
- Targeted physical exam will be done only as dictated by a change in medical history.
- A urine pregnancy test will be performed on all female participants of childbearing potential

for any visit longer than 14 days from the last pregnancy test..

- Follow-up visits were also halted, which impacted several participants' Day 180 follow-up visit.
- We are requesting that the windows for the Day 180 visit be extended by 90 days.
- Extending the window for the Day 180 follow-up visits would allow samples from participants whose visits were halted at this time point to be collected once the Emory restrictions regarding COVID-19 are lifted and staff can reasonably collect samples, dependent upon when the University and applicable Unit and School allow. The scientists feel that the samples, even if a few months late, will greatly help evaluate the longevity of the responses to flu vaccines.
- Study activities will not be changed, just the timing of the Day 180 visit.

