#### **7.5 Unscheduled Visit**

Unscheduled visits are not anticipated with this study, but may occur at any time during the study. Any of the following activities may be performed:

- Medical history will be reviewed and updated as appropriate.
- All concomitant medications taken since the study visit will be recorded on the appropriate data collection form. Previously recorded medications will be updated as appropriate.
- Study personnel will discuss with participants and assess and record all AE/SAEs. Previously recorded AE/SAEs will be updated as appropriate.
- Vital signs, including oral or axillary temperature, pulse, blood pressure and will be obtained.
- A targeted physical examination will be performed by a study clinician licensed to make medical diagnoses and listed on the Form FDA 1572 as the site principal investigator or sub-investigator.

- Approximately 10 mL of venous blood will be collected for chemistry and/or hematology performed by the local or site laboratory if deemed necessary by [name] or a designee.
- A urine pregnancy test will be performed on all female participants of childbearing potential.

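### The 432 mL blood limit in Section 2.3.1 is the sum of the Day 0–180 research draws alone, so the screening draw and any unscheduled draw can take a participant over it

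*Combined protocol and SAP*

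**What the plan says.** Section 2.3.1 (Potential Risks) names iron deficiency anemia as a risk of repeated blood drawing. The control it gives is that "no more than 432 ml of blood will be obtained over a period of 180 days". The sentence refers to blood in general, not research blood, and does not say when the 180 days begin.

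The other statements about volume are:

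- The Study Summary says "Approximately 450 ml of blood will be collected for the research assays during the course of the study". It then itemizes 16 mL at screening, 48 mL at enrollment, 96 mL at Days 7 and 14, and 64 mL at Days 28, 90 and 180. The design schematic and Section 8.1 give the same volumes.
- Section 7.1 describes the screening draw: "Approximately 16 ml (about 1 tablespoon) of venous blood will be collected for chemistry and hematology performed by the site laboratory". It is taken 1 to 30 days before vaccination.
- Section 7.3 provides for "five follow up visits, with the respective window periods, per the table below". The Day 180 window is plus or minus 14 days, and a 90-day expansion is being requested for visits delayed by the pandemic.
- Section 7.5 says "Unscheduled visits are not anticipated with this study, but may occur at any time during the study". At such a visit, "Approximately 10 mL of venous blood will be collected for chemistry and/or hematology", if the investigator or a designee considers it necessary. The section does not cap the number of these visits.

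**The concern.** Section 2.3.1 is worded as a hard maximum on all blood, but the figure is the total for one category of draw. The screening draw is mandatory and the unscheduled draw is expressly allowed, yet neither has room under the limit.

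Two things are at stake. First, a figure offered to participants and the review board as protection against a named harm understates the blood that may be taken. Second, staff who follow Section 7.5 can breach Section 2.3.1, and Section 14.6 counts any noncompliance with the protocol as a deviation.

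The Summary's total of about 450 mL does not match 432 mL. It matches the total with screening, but it is described as blood for research assays although 16 mL of it is for clinical chemistry and hematology.

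**Working it through.** **Inputs.** Research draws: 48 mL (Day 0), 96 mL (Day 7), 96 mL (Day 14), and 64 mL each at Days 28, 90 and 180 (Study Summary, Sections 7.3 and 8.1). Screening: 16 mL, on Day −30 to Day −1 (Section 7.1). Unscheduled: about 10 mL per draw (Section 7.5). Last visit: Day 166 to Day 194 under the standard window (Section 7.3).

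**Step 1. Reproduce the plan's figures.**

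- Research blood: 48 + 96 + 96 + 64 + 64 + 64 = 432 mL. This is exactly the limit in Section 2.3.1, so the margin is 432 − 432 = 0 mL.
- Scheduled blood including screening: 432 + 16 = 448 mL. This agrees with the Summary's approximate 450 mL.

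**Step 2. Count the period as Day 0 to Day 180.** Screening falls outside it.

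- All visits on nominal days: 432 mL. The limit is met exactly.
- One unscheduled draw, last visit on or before Day 180: 432 + 10 = 442 mL. The limit is exceeded.
- Last visit on Day 181–194: Day 0–180 holds 432 − 64 = 368 mL, or 378 mL with one unscheduled draw. The limit is kept.

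**Step 3. Count any 180 days, from first to last draw.** Suppose screening is s days before Day 0 and the last visit is on Day v. All scheduled blood then falls within 180 days when s + v ≤ 180.

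- Nominal last visit (v = 180): this would need s ≤ 0, but s is at least 1. Screening falls outside and the total stays at 432 mL.
- Last visit on Day 166–179: the condition is s ≤ 180 − v. That runs from s ≤ 14 (v = 166) to s = 1 (v = 179). Examples are Day −14 with Day 166 (14 + 166 = 180) and Day −1 with Day 179 (1 + 179 = 180). The total is 448 mL.
- The same, with one unscheduled draw: 448 + 10 = 458 mL.

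**Step 4. Size of the excess over 432 mL.**

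| Case | Total | Excess | Percent |
|---|---|---|---|
| One unscheduled draw, no screening | 442 mL | 10 mL | 10/432 = 2.3% |
| Screening, no unscheduled draw | 448 mL | 16 mL | 16/432 = 3.7% |
| Screening and one unscheduled draw | 458 mL | 26 mL | 26/432 = 6.0% |

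**The case against.** The best defense is that 432 mL is correctly added and that the most natural counting period is Day 0 to Day 180. On that reading screening is outside, nominal conduct complies, and only an unscheduled draw breaks the limit. Such visits are not expected. The draw is taken only when judged necessary, and it can include hemoglobin, so it may itself detect anemia. The visit volumes are all approximate, and the 16 mL is disclosed in several places. All of this stands, and it keeps the point minor. It does not make the limit one that the design guarantees, because a permitted draw still gives 442 mL and the sentence is not confined to research blood or to Day 0–180.

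Three stronger readings are tempting, and the documents do not support them.

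- **Every participant who gives all scheduled draws breaches the limit, at 448 mL.** A reader might infer this because the synopsis gives participant duration as 180 days. Screening is 1 to 30 days before Day 0, so screening to a nominal Day 180 spans 181 to 210 days. A 180-day duration fits Day 0–180 and does not place screening inside the limit period.
- **The stated volume is the main protection against anemia after vaccination.** Appendix A does list hemoglobin only at screening and unscheduled visits. But Section 5.1 screens hemoglobin at entry, Section 5.3 stops blood draws in anyone who develops an exclusion criterion, and Section 7.3 requires review of medical history and adverse events at every follow-up visit.
- **Re-enrollment makes the excess much larger.** Section 5 says "Individuals who complete the study will be given the option to re-enroll in subsequent years". Stacking two enrollments needs a rolling limit across enrollments, which the protocol does not state, and unusually short gaps between vaccinations. With vaccinations 365 days apart and nominal visits, a 180-day period that includes the first Day 180 draw ends by Day 360, before the second vaccination. It can hold that draw and at most the second screening draw: 64 + 16 = 80 mL.

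**Conclusion.** The concern holds as a minor inconsistency in a safety statement. The limit equals the scheduled research blood, omits 16 mL of mandatory screening blood and any unscheduled draw of about 10 mL, and can be exceeded by permitted conduct. It is exceeded by 10 mL when counted from Day 0 to Day 180 with one unscheduled draw and a last visit by Day 180. It is exceeded by 16 mL, or 26 mL with one unscheduled draw, when an early last visit and a close screening draw fall within the same 180 days.

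These sizes assume that the volumes are taken as stated, that all scheduled draws are given, and that there is at most one unscheduled draw; each further one would add about 10 mL. The second case also assumes that the 180 days may start before Day 0, which the text neither says nor rules out. The documents do not indicate how often either case would occur. No endpoint or analysis is affected.

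**What to change.** In Section 2.3.1, restate the figure as 432 mL of research blood from Day 0 to the final visit plus 16 mL of screening blood, 448 mL scheduled in total. Say that any unscheduled clinical draw of about 10 mL is in addition. Naming Day 0 to the final visit also settles the counting period and covers early and late last visits. In the Study Summary, label the approximate 450 mL as total blood including screening, not as blood for research assays.

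The cost is two wording changes, plus the consent form if it repeats the 432 mL figure; the form was not among the documents reviewed. The one downside is that the stated maximum looks slightly less favorable. Visits, draw volumes and the analysis stay as they are.
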